#### **15.6.4 Data Provided to Data Monitoring Committee**

The Data Monitoring Committee will receive a statistical report. The details on the content of the report will be described in the Data Monitoring Committee charter.

#### **15.6.5 Stopping Rule**

The study will not be stopped for overwhelming effectiveness reasons. However, the Data Monitoring Committee may recommend stopping the study for safety reasons at any time during the trial. The Investigator may decide to stop the study for reasons described in Section 14.2.1. The Sponsor may also decide to stop the study for safety or other reasons at any time during the trial (see Section 22.1).

#### **15.6.6 Stopping Rule Provided to Sponsor by Data Monitoring Committee**

The Data Monitoring Committee will make recommendations to the Sponsor on the sample size adjustment and any safety concerns.

---

### **15.6.7 Type I Error Rate Adjustment**

There will be no type I error rate adjustment as there is no intention to stop the study for effectiveness benefit. In addition, the sample size is planned to be increased when the interim CP is promising and this will protect the type 1 error rate (18).

## **15.7 General Statistical Considerations**

All collected study data will be presented in subject data listings. Statistical analyses will be performed using SAS® for Windows, version 9.3 or later. Descriptive statistics (number of observations, mean, SD, median, minimum, and maximum values) will be calculated by treatment arm for continuous variables. Frequencies and percentages will be presented by treatment arm for categorical variables.

### **15.7.1 Analysis Populations**

#### ***15.7.1.1 Intention-to Treat Population***

The ITT population is defined as all randomized subjects.

#### ***15.7.1.2 Per Protocol Population***

The per protocol (PP) population refers to all randomized subjects who were successfully randomized, treated, and stayed on their assigned treatment with no major protocol deviation.

#### ***15.7.1.3 Safety Population***

The safety population is defined as any subject receiving the treatment after randomization. This population will be used for the analysis of safety parameters.

### **15.7.2 Covariates**

For effectiveness analyses, the stratification factors and the respective baseline values for the endpoint will be used as covariates in the analysis models.

### **15.7.3 Missing Data**

For effectiveness evaluation, missing data points will be imputed using multiple imputation approach. This approach is robust and the least biased for the missing at random cases. This method will be detailed in the SAP.

### **15.7.4 Multiple Comparisons and Multiplicity**

For the co-primary endpoints, there will be no type I error adjustment.

For the secondary endpoints, the Closed Test procedure will be used. All the secondary endpoints will be ordered prior to database lock and tested according to the order.

---

### **15.7.5 Subgroup Analysis**

Several subgroup analyses will be conducted for the stratification factors as well as the pre-specified secondary endpoints. Subgroup analyses will also be performed based on the results of serum amylase and genomic tests. The detail of these subgroup analyses will be presented in the SAP.

## **15.8 Statistical Methods**

A SAP will be developed and approved before the database is locked. The SAP will present the detailed statistical methodology to be used in analyzing the effectiveness and safety data from this trial.

All the effectiveness endpoints presented here will be conducted using both the ITT and the PP populations. All safety analyses will be conducted using the safety population.

All data collected will be summarized according to the variable type:

- Continuous data summaries will include:
  - Number of observations, mean, SD, median, minimum, and maximum values
  - ANCOVA with the stratification factors and the respective baseline values for the endpoint in the model for inferential statistics
- Categorical data summaries will include:
  - Frequency counts and percentages
  - Logit model with the stratification factors and the respective baseline values for the endpoint in the model for inferential statistics
- Time-dependent data:
  - Cox proportional hazards model will be used to analyze time-dependent data
  - Kaplan-Meier will be used to depict the time to event data

### **15.8.1 Subject Disposition**

The disposition of all subjects who sign an Informed Consent Form will be provided. The numbers of subjects screened, randomized, completed, and discontinued during the study, as well as the reasons for all post-randomization discontinuations will be summarized by treatment arm. Disposition and reasons for study discontinuation will also be provided as a by-subject listing.

---

### **15.8.2 Demographics and Baseline Characteristics Analysis**

Demographic and baseline characteristic data will be summarized descriptively and/or presented as a by-subject listing for the safety population. In addition, all the known potential risk factors (e.g., diabetes, dyslipidemia, hypertension) will be tabulated and compared between the two treatment arms.

### **15.8.3 Extent of Exposure to Study Product**

Extent of exposure to the study product will be summarized for each arm.

### **15.8.4 Compliance with Diet, Life-Style, and Study Product**

Compliance with the diet and life-style recommendations and the intake of the study product will be summarized for each arm.

### **15.8.5 Concomitant Medications/Therapies**

Concomitant medications/therapies will be summarized separately for the safety population. All prior and concomitant medications recorded in the electronic CRF will be coded to all matching Anatomic Therapeutic Classification codes using the most recent version of WHO Drug version. Descriptive summaries, by treatment arm, will be prepared using the coded term. All concomitant medications/therapies recorded in the electronic CRF will be listed.

### **15.8.6 Effectiveness Analysis**

#### ***15.8.6.1 Primary Analysis***

The primary analysis will be conducted on the ITT population.

#### **Co-primary endpoints**

ANCOVA will be used to compare the percent change in weight from baseline to Day 171 for the two treatment arms. The stratification factors and baseline weight will be included in the analysis and associated treatment difference, 95% confidence interval around the difference and *P* value for the treatment effect will be reported.

The proportion of body weight responders will be presented descriptively by treatment arm. Responders in this case will be defined as those subjects who have achieved  $\geq 5\%$  reduction in body weight compared to baseline. In addition, the Logit model will be used to analyze the percent of responders, with the stratification factors and baseline weight in the model.

To maintain the trial-wise type I error rate at 0.05, a closed test procedure will be used for the secondary and tertiary endpoints. The order of the endpoints will be as follows:

---

### **Secondary and tertiary endpoints**

Analysis of the secondary and tertiary endpoints will be summarized according to the variable type:

- continuous data summaries will be based on ANCOVA or Mixed Model using the stratification factors and the respective baseline values for the endpoint as a covariate in the model
- categorical data summaries will be based on Logit model using the stratification factors and the respective baseline values for the endpoint as a covariate in the model

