## **5. INTRODUCTION AND RATIONALE**

### **5.1 Disease Background**

Overweight (body mass index (BMI)  $\geq 25$  and  $< 30$ ) and obesity (BMI  $\geq 30$ ) are becoming major health problems worldwide (1). The overweight/obesity epidemic was first noted in US and then spread to other industrialized nations; it is now being seen even in developing countries (2). The World Health Organization (WHO) estimated that the worldwide prevalence of obesity has nearly doubled between 1980 and 2008. In 2008, approximately 500 million adults around the globe were obese and in 2014, this number reached 600 million.

Overweight and obesity are responsible for increased morbidity and mortality (3). The comorbid conditions associated with overweight/obesity include cancer, coronary heart disease, delayed puberty, depression, disability, dyslipidemia, gallbladder disease, gout, hypertension, liver disease, osteoarthritis, respiratory dysfunction, sleep apnea, sexual impairment, social discrimination, type 2 diabetes, and other practical limitations and challenges. Weight loss of at least 5 to 10% appears to lower the risk of many of these comorbidities (4).

Overweight and obesity are chronic conditions and this characteristic should be considered when facing overweight and obese individuals. Management of overweight and obesity includes hypocaloric diet, exercise, behavior modification, device (e.g., intragastric balloon), drug, and surgery (bariatric surgery) (1, 5, 6, 7). The therapeutic benefit of all currently available anti-obesity tools is limited by their marginal efficacy, variable tolerability and safety profiles, and poor compliance.

The intragastric balloon is an intervention designed to reduce stomach volume (7), but there are conflicting data on sustained weight loss and no clear data indicating a decrease in mortality. Side effects include balloon movement, nausea, vomiting, pain, and stomach ulceration.

The results from bariatric surgery suggest that limiting the functional volume of the stomach is an effective modality for the treatment of obesity (6). However, because of the risk of peri-operative complications and the relatively high cost, bariatric surgery is usually reserved for the severely obese subjects.

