## **8.3 Inclusion Criteria**

1. Male and female ambulatory subjects (it is recommended to have at least 45% of each gender)
2. Age  $\geq$  22 years and  $\leq$  65 years
3. BMI  $\geq$  27 and  $\leq$  40 (it is recommended to have at least 70% of subjects with BMI  $<$  35 and body weight  $<$  120 kg in at least 92% of all subjects; subjects with BMI  $<$  30 should have at least one comorbidity including untreated or metformin-treated type 2 diabetes, untreated dyslipidemia with low-density lipoprotein (LDL) cholesterol  $\geq$  130 mg/dL ( $\geq$  3.37 mmol/L) and/or triglycerides  $\geq$  150 mg/dL ( $\geq$  1.69 mmol/L) or drug-treated dyslipidemia, and untreated hypertension with supine systolic blood pressure (SBP)  $\geq$  140 mm Hg and/or supine diastolic blood pressure (DBP)  $\geq$  90 mm Hg based on the mean of two consecutive readings or drug-treated hypertension)
4. Fasting plasma glucose  $\geq$  90 mg/dL and  $\leq$  145 mg/dL ( $\geq$  5.0 mmol/L and  $\leq$  8.1 mmol/L); it is recommended to have approximately 45 to 55% non-diabetic normoglycemic subjects (fasting glucose  $\geq$  90 mg/dL and  $<$  100 mg/dL or  $\geq$  5.0 mmol/L and  $<$  5.6 mmol/L) and the rest, non-diabetic impaired fasting glucose subjects (fasting glucose  $\geq$  100 mg/dL and  $<$  126 mg/dL or  $\geq$  5.6 mmol/L and  $<$  7.0 mmol/L) or diabetic subjects either:
  - untreated (fasting glucose  $\geq$  126 mg/dL and  $\leq$  145 mg/dL or  $\geq$  7.0 mmol/L and  $\leq$  8.1 mmol/L)
  - or metformin-treated (metformin dose  $\leq$  1500 mg/day, fasting glucose  $\leq$  145 mg/dL or  $\leq$  8.1 mmol/L)
5. Ability to follow verbal and written instructions
6. Informed Consent Form signed by the subjects

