### **11.1.3 Tertiary Endpoints**

- Body weight responders ( $\geq 10\%$  weight loss from baseline to Day 171)
- Estimated excess body weight (percent change from baseline to Day 171)
- Body weight status (normal, overweight, obese) (change from baseline to Day 171)
- Waist circumference (change from baseline to Day 171)
- Serum insulin (percent change from baseline to Day 171)
- Serum C-reactive protein (CRP) (change from baseline to Day 171)
- Serum total cholesterol (percent change from baseline to Day 171)
- Serum LDL cholesterol (percent change from baseline to Day 171)
- Serum high-density lipoprotein (HDL) cholesterol (percent change from baseline to Day 171)
- Serum total cholesterol/HDL cholesterol ratio (change from baseline to Day 171)
- Serum triglycerides (percent change from baseline to Day 171)
- Supine and standing SBP and DBP (change from baseline to Day 171)
- Food intake (change from baseline to Day 169)
- Food habits (change from baseline to Day 169)
- Satisfaction (overall impression on Day 169)
- Impact of weight on quality of life (IWQOL) (change from baseline to Day 171) (at selected sites)

The secondary and tertiary effectiveness endpoints are for supportive purposes only.

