## **15.4 Sample Size Determination and Rationale**

For this clinical trial, a total of 460 subjects (230 per arm) will be randomized to have 322 subjects complete the study (161 per arm) due to an anticipated dropout rate of 30%. This sample size will allow establishing both super-superiority and superiority with sufficient statistical power based on the primary endpoint of change in body weight from baseline.

The sample size calculation, using PASS (16), is based on the assumption that there will be a clinically meaningful difference of at least 3.0% weight loss between the two arms after 24 weeks of treatment. This 3.0% is also being used as margin to establish the super-superiority (lower bound of the confidence interval of Gelesis100 effect  $\geq 3.0\%$  of placebo effect). With the above sample size, there is 85% statistical power for a 3.0% margin super-superiority (i.e., delta of at least 4.5%) with a common SD of 5.0% and a type I error rate of 0.05 (one-sided test). The statistical formula for the study hypothesis is as follows:

$$H_0: \mu_{\text{placebo}} - \mu_{\text{Gelesis100}} < 3.0\%$$

$$H_A: \mu_{\text{placebo}} - \mu_{\text{Gelesis100}} \geq 3.0\%$$

Where  $\mu_{\text{placebo}}$  is the mean percent change from baseline in the placebo arm and  $\mu_{\text{Gelesis100}}$  is the mean percent change from baseline in the Gelesis100 arm.

In addition, with the above sample size, there will be at least 90% statistical power to establish that the difference between the two arms is greater than 0 (i.e., the superiority with no margin), with a common SD of 5.0% and a type I error rate of 0.05 (two-sided tests), with the null hypothesis that the mean percent change from baseline in primary effectiveness endpoint is the same for both treatment arms and the alternative hypothesis that the Gelesis100 arm provides a different mean percent change in body weight than does the placebo arm. The statistical formula for the study hypothesis is as follows:

$$H_0: \mu_{\text{placebo}} - \mu_{\text{Gelesis100}} = 0$$

$$H_A: \mu_{\text{placebo}} - \mu_{\text{Gelesis100}} \neq 0$$

Where  $\mu_{\text{placebo}}$  is the mean percent change from baseline in the placebo arm and  $\mu_{\text{Gelesis100}}$  is the mean percent change from baseline in the Gelesis100 arm.

---

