### **15.5.2 Stratification**

The following characteristics at the Screening Visit will be used as stratification factors at the time of randomization and the centralized randomization procedure will balance treatment arm assignments in each country or combination of countries for the following stratification factors:

- male, BMI < 35, and normal fasting glucose
- male, BMI < 35, and impaired/diabetic fasting glucose
- male, BMI  $\geq$  35, and normal fasting glucose
- male, BMI  $\geq$  35, and impaired/diabetic fasting glucose
- female, BMI < 35, and normal fasting glucose
- female, BMI < 35, and impaired/diabetic fasting glucose
- female, BMI  $\geq$  35, and normal fasting glucose
- female, BMI  $\geq$  35, and impaired/diabetic fasting glucose

The selection of these stratification factors is based on the facts that gastric capacity has a tendency to be higher in male subjects and in subjects with higher BMI, and weight loss can be more important in subjects with higher fasting glucose (data from the FLOW study).

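### The Logit model for body weight status uses baseline class and a BMI split at 35 but not continuous baseline BMI; adding it gains about 6 to 14 points of power at a true difference of 2%, and little at 4.5%

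*Combined protocol and SAP*

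**What the plan says.** Section 11.1.3 lists as a tertiary endpoint "Body weight status (normal, overweight, obese) (change from baseline to Day 171", and closes by giving all secondary and tertiary endpoints a supportive role only. Section 5.1 puts overweight at BMI 25 to below 30 and obesity at 30 or more. Section 8.3 admits BMI 27 to 40, and "it is recommended to have at least 70% of subjects with BMI" below 35.

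The model comes from Section 15.8.6.1, Secondary and tertiary endpoints: "categorical data summaries will be based on Logit model using the stratification factors and the respective baseline values for the endpoint as a covariate". Sections 15.7.2 and 15.8 give the same general rule. The stratification factors in Section 15.5.2 cross gender, screening BMI below 35 or not, and fasting glucose status; the first stratum reads "male, BMI < 35, and normal fasting glucose". No section names continuous baseline BMI as a covariate for body weight status. By contrast, the Logit model for the co-primary 5% responder endpoint is given baseline weight.

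On multiplicity, Section 15.8.6.1 says that "a closed test procedure will be used for the secondary and tertiary endpoints" and announces an order, but the text lists none. Section 15.7.4 applies the procedure to the secondary endpoints only. Sections 15 and 15.8 leave detailed methods to a separate SAP, to be approved before database lock.

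**The concern.** Whether a subject changes class depends on two things: the percentage of weight lost, and how far baseline BMI lies above 30 or 25. The second is known exactly at entry. The plan's general rule reduces it to a two-level class plus a split at 35, so subjects with very different thresholds are treated as equally likely to change class. Leaving out a strong prognostic variable in a Logit model does not invalidate the test of treatment, but it costs power.

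At stake is the sensitivity of one supportive tertiary comparison. If body weight status also sits in a fixed testing sequence, a needlessly weak test there could keep later endpoints from being tested.

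**Working it through.** **1. The plan's own power figure.** Section 15.4 has 161 completers per arm, SD 5.0%, true difference 4.5%, margin 3.0%, one-sided 0.05. The standard error is 5 × √(2/161) = 0.557. Then (4.5 − 3.0)/0.557 − 1.645 = 1.05, and Φ(1.05) = 85%. The stated 85% reproduces, and 161/(1 − 0.30) = 230 per arm. The plan gives no power for body weight status.

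**2. What the model sees.** With cut-offs at 25 and 30 and entry at 27 to 40, nobody starts in the normal class. Baseline class and the split at 35 give three bands. Loss needed to leave the obese class is 1 − 30/BMI; to reach normal it is 1 − 25/BMI.

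| Band | Loss needed to improve by one class |
|---|---|
| 27 to 30 | 7.4% (BMI 27) to 16.7% (near 30) |
| 30 to 35 | just above 0% (BMI 30) to 14.3% (near 35) |
| 35 to 40 | 14.3% (BMI 35) to 25% (BMI 40) |

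**3. Why this matters within a band.** Assume a 3% mean placebo loss and SD 5%. At BMI 31 the threshold is 3.2%, so the chance of improving is P(Z > (3.2 − 3)/5) = about 48%. At BMI 34 the threshold is 11.8%: P(Z > (11.8 − 3)/5) = about 4%. The planned model gives both placebo subjects the same probability if gender and glucose status match.

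**4. Simulation of the power cost.** Inputs from the documents: entry range, cut-offs, the split at 35, SD 5%, two-sided 0.05, 161 or 230 per arm, and the pilot (FLOW) study's 2.0% difference and 4.1% placebo loss (Section 5.2.1.2). Assumed: the shape of the BMI distribution, the other placebo losses, normal percent weight change, and the outcome coded as improvement by at least one class. Compared: the model as written (class, gender, glucose status, BMI split at 35) and the same model plus continuous BMI. Results below use 2,000 trials per scenario and likelihood-ratio tests; simulation error is about 1 point.

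| True difference; placebo loss | BMI assumption | Per arm | As written | Plus BMI | Gain |
|---|---|---|---|---|---|
| 2%; 4.1% | pilot-like, mean 31.7, SD 2.4 | 161 | 51.8% | 64.0% | 12.2 |
| 2%; 4.1% | mean 33, SD 3 | 161 | 44.8% | 56.4% | 11.6 |
| 2%; 4.1% | uniform, 70% below 35 | 161 | 40.4% | 50.3% | 9.9 |
| 2%; 4.1% | mean 33, SD 3 | 230 | 56.6% | 69.4% | 12.8 |
| 3%; 4.1% | mean 33, SD 3 | 161 | 78.1% | 88.1% | 10.0 |
| 3%; 4.1% | uniform, 70% below 35 | 161 | 72.8% | 84.8% | 12.0 |
| 3%; 4.1% | mean 33, SD 3 | 230 | 91.0% | 97.4% | 6.4 |
| 4.5%; 3% | mean 33, SD 3 | 161 | 98.5% | 99.9% | 1.4 |
| 4.5%; 3% | uniform, 70% below 35 | 161 | 97.0% | 99.2% | 2.2 |

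Across this run the gain at 3% ranged from 4 to 12 points. With no true effect, rejection stayed near 5% with or without BMI (4.8 to 6.0%).

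**5. Sensitivity.**
- A second simulation (1,500 trials; placebo loss 2, 3 or 4.1%; 70 to 84% of subjects below BMI 35) gave gains of about 6 to 13 points at 2% and 4 to 12 at 3%. The smallest gain at 2% was from 33% to 39% with 322 subjects. Null rejection was 4.0 to 4.8%.
- A third simulation gave about 8 to 14 points at 2%, 5 to 11 at 3% and 0 to 3 at 4.5%.
- A three-level proportional-odds model (600 trials, error about 2 points) gave 11.5 to 14 points at 2%, 2 to 10 at 3%, and 0 to 1 at 4.5%.

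**The case against.** **BMI is already in the model.** A reader might infer from the two-level class that BMI is ignored. The documents do not support that: the stratification factors bring in the split at 35. Against a class-only model the gain at 1.5 to 2% would look larger, about 10 to 20 points. The table above counts only the gain beyond the split.

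**The rule may already mean BMI.** The responder Logit model carries baseline weight, so the baseline value for a class derived from BMI could be read as BMI itself. Details are also left to the SAP. This stands in part: if the SAP names continuous BMI, the point is met. The literal reading of the general rule is still the class, so the covariate needs naming.

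**The gain is selective.** This stands. The 2.0% difference comes from a 12-week pilot with a larger calorie deficit (600 against 300 kcal/day). The trial is sized for 4.5%, where power for this endpoint is already 97% or more. At a true 2%, the co-primary test against the 3.0% margin would succeed with probability P(Z > 1.645 + 1/0.557), about 0.03%. If that test gates later ones, which the documents do not state, formal testing of body weight status would be moot at 2%.

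**It is not entirely free.** Adding a prognostic covariate changes the conditional odds ratio being estimated. This stands, and is a reason to fix the choice in advance.

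**A weak test could stall the sequence.** A reader might infer this from the closed test wording. Section 15.7.4 applies the procedure to secondary endpoints only, and no order is listed, so body weight status may be last or outside it.

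**Conclusion.** The point holds as a matter of efficiency. As written, the model uses baseline class and a split at 35, and leaves out the continuous baseline BMI that sets each subject's threshold. Adding it raises power by roughly 6 to 14 points at a true difference of 2%, 4 to 12 at 3%, and 0 to 3 at 4.5%. Type I error is materially unchanged, at about 4 to 6% in the simulations.

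These sizes rest on assumed BMI distributions within 27 to 40, placebo loss of 2 to 4.1%, SD 5% and improvement by at least one class as the outcome; the proportional-odds check agrees in direction, with a smaller lower end at 3%. Multiple imputation of all randomized subjects would put the effective size somewhere between the 161 and 230 per arm simulated.

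The planned analysis is valid, and no primary or safety conclusion is touched. The impact is confined to a supportive tertiary endpoint; any knock-on effect depends on a testing order that the documents do not list.

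**What to change.** In Section 15.8.6.1 (and 15.7.2), or in the SAP, specify that the Logit model for body weight status includes continuous baseline BMI in addition to baseline class and the stratification factors. State that the treatment odds ratio is then conditional on BMI. Settle this before unblinding, since the choice of covariates affects both the estimate and its P value.

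The cost is one covariate in one model and a sentence of text. No extra subjects, visits or measurements are needed: height is taken at screening, and weight at screening and baseline.
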